6.4 Exploratory Analyses for Main Study

In addition to the primary, secondary and tertiary analyses supported by the described adjusted analyses, exploratory subgroup analyses will be conducted to determine whether any of these factors can modify the effect of the nerinetide vs. placebo treatments. Sub-group analyses will be performed on the primary estimand as well as the secondary estimands that are not considered exploratory following the fixed sequence multiple testing procedure described in Section 6.2. In addition, forest plots will be generated to display effect sizes by sub-group⁶. They will be reported by randomization strata if the interaction term in the primary pivotal analysis plus the interaction term is significant at the 0.05 level.

Dichotomous sub-groups of interest include the following:

- Age (<80 years vs \geq 80 years of age)
- Age (<65 years vs \geq 65 years of age)
- Sex (men vs. women)
- Ethnicity (Hispanics vs non-Hispanic)
- Race (White, Asian, Black, Other)
- Baseline stroke severity (NIHSS > Median vs. NIHSS <= Median)
- Baseline occlusion location (MCA [including M1 and M2] vs. ICA)
- Baseline ASPECT score (5-7 vs. 8-10)
- Time from qualifying imaging to study drug initiation (greater than vs. less than the median).
- Time from onset of stroke symptoms to start of study drug greater than vs. less than the median).
- Degree of reperfusion (TICI ³ 2b vs. TICI <2b)
- Subjects weighing between 105-120 kg.

Additional sub-groups may be examined, but those specified above are of prior clinical interest.

Effect sizes will be estimated as subgroup-specific odds ratios ($\pm 95\%$ CIs) as follows. Separate logistic regression models for the primary/secondary endpoints, with treatment group and the stratification variables and covariates used in the minimization algorithm as predictors, will be fit to each of the subject subgroups (e.g., a model will be fit to males and a second model will be fit to females). The estimated (nerinetide/placebo) odds ratios, with 95% confidence intervals will be the nerinetide effect size estimates for each of the subgroups (e.g., for males and for females) and will be displayed in the forest plots.

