	odds ratio (95% CI). Modified Rankin scores of 5 and 6 (bed-bound with severe disability, and death) will be collapsed into a single category representing severely limited functioning. An adjusted POM will be used to derive the common odds of improvement (i.e. the nerinetide vs. placebo "shift" in mRS score distributions). Adjustment of the treatment effects will include the same set of variables as used for the logistic regression model for the primary estimand. Deceased participants will be included with a mRS score of 6.
	Since the analysis of the ordinal mRS scores will employ a proportional odds model (POM), if test of the proportional odds assumption shows the assumption to be invalid, this secondary analysis will be removed from the fixed sequence testing procedure and conducted as an exploratory analysis instead.
	NIHSS scores at Day 90 will be dichotomized into 0-2 (indicating a good neurological outcome) versus >2 (indicating otherwise). Deceased participants will be included with a NIHSS score of 42. The proportion of participants achieving a good neurological outcome at Day 90 in nerinetide versus placebo control participants will be analyzed. Results will be summarized and tabulated.
Tertiary	Total volume of new strokes on MRI or CT brain imaging in the nerinetide versus placebo control participants. Total volume will be assessed using an unadjusted two-tailed Student's t-test and supported by an adjusted analysis comprising of a linear regression that includes the stratification and minimization variables. A cubic root transformation will be performed if needed. Results will be reported with confidence intervals for the unadjusted and adjusted treatment effect between treatment groups.
	Barthel, Day 90 mRS≤1, Day 90 mRS 4-6 , the tertiary outcomes comprising proportions of responders will be analyzed similarly to the primary efficacy analysis. Deceased participants will be included in the ITT population with a Barthel Index score of 0.
	EQ-5D-5L will be assessed descriptively. Results will be summarized and tabulated.
Exploratory	Exploratory subgroup analyses will be conducted to determine whether any of these factors can modify the effect of the nerinetide vs. placebo treatments. Sub-group analyses will be performed on the primary outcome and include forest plots to display effect sizes by sub-group ⁶ .

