4.6 Pooling of Data from the Two Time-to-Randomization Strata

Since the randomization will be stratified by time from stroke onset to randomization \leq 4.5 hours (yes/no), the assessment for treatment-by-stratification variable interaction to examine for effect modification will be performed via a log-binomial generalized linear model as described in Section 6.1.3. In addition, homogeneity of the randomization stratification factor will be tested via Breslow-Day statistic²². If there is no evidence for effect modification, then we will report the data for the entire cohort only. If there is evidence for effect modification, the effect size for the primary, secondary and tertiary outcomes will be additionally reported by stratum.

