6.1.3 Primary Efficacy Estimand Analysis

Primary statistical analysis for primary estimand

The primary analysis for the primary estimand will be conducted in the ITT population according to the randomized treatment. Missing data will be imputed following the single imputation approach in Section 4.3.2.

The primary hypothesis to be tested is that administration of nerinetide will result in an increase in the proportion of mRS responders (as defined by a score of 0-2) at Day 90.

The pivotal primary analysis will be conducted on the ITT population at the 2-sided 0.05 significance level overall (for the trial), adjusted for the interim analysis per the O'Brien-Fleming boundary spending function.

The pivotal main effects primary analysis will use a multivariable generalized linear model (GLM) using a binomial distribution with a log link to provide adjusted relative risk (log-binomial regression). Adjustment will include the stratification covariate of time from stroke onset to randomization \leq 4.5 hours (yes/no) and the randomized minimization (age, sex, baseline NIHSS score, baseline ASPECT score, occlusion location, time from qualifying imaging to randomization and pooled site).

The main effects primary analysis will be supported by a further analysis in which the GLM used for the pivotal analysis also includes the interaction term (treatment by randomization stratification factor). If the interaction term is significant at the 0.05 level, we will additionally

Version: 2.0	SAP NA-1-009
Date: 18 November 2021	NoNO Inc

repeat the primary analysis, sensitivity analyses, the supportive analyses described below, and the analyses for the secondary efficacy estimand analyses and tertiary efficacy outcome analyses for each stratum separately. If the interaction term is not significant at the 0.05 level, the data for each stratum will not be reported separately.

If a binomial distribution model fails to converge, accepted methods using multivariable logistic or Poisson regression with robust error variance will be used to provide adjusted relative risk.

Example SAS code for the log-binomial regression model as follows:

```
PROC GENMOD DATA = ADMRS;
CLASS TRTPN RANDTIME SEX BASPECT OCCLOC SITEGR1;
MODEL CRIT1FN(event="1") = TRTPN RANDTIME AGE SEX BNIHSS
BASPECT OCCLOC IMA_TIME SITEGR1 / DIST = BINOMIAL LINK=LOG;
ESTIMATE "NA-1 vs. placebo" TRTPN 1 -1 / exp;
```

RUN;

Example SAS code for the Poisson regression model:

```
PROC GENMOD DATA = ADMRS;

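### SAP 6.4 asks which factors modify the treatment effect but plans no treatment-by-factor estimate or test for any factor on its list

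*Combined protocol and SAP*

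**What the plan says.** The aim is stated in SAP 6.4: "exploratory subgroup analyses will be conducted to determine whether any of these factors can modify the effect of the nerinetide vs. placebo treatments". Protocol Table 9-1 (section 9.3.2) gives the same aim.

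The method in SAP 6.4 is "Separate logistic regression models for the primary/secondary endpoints", fitted within each level of each factor and adjusted for the stratification variable and the minimization covariates. On output, it says "Effect sizes will be estimated as subgroup-specific odds ratios", with 95% confidence intervals, displayed in forest plots. The protocol adds only this: "Sub-group analyses will be performed on the primary outcome and include forest plots to display effect sizes by sub-group".

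The SAP 6.4 list has 12 factors: two age cuts, sex, ethnicity, race (four levels), NIHSS, occlusion location, ASPECTS, two time intervals, reperfusion and weight 105-120 kg. The weight entry has no comparison group in the SAP; the protocol gives one (105 kg or less).

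Interaction is tested elsewhere, for one factor only: time from onset to randomization, 4.5 hours or less.
- SAP 6.1.3 adds that interaction in a supportive model, and protocol Table 9-1 puts it in the primary model.
- SAP 4.6 says "homogeneity of the randomization stratification factor will be tested via Breslow-Day statistic", and SAP 6.1.3 repeats that test.

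This stratum is on the protocol's subgroup list but not on the SAP's. SAP 6.4 does mention an interaction term, but it is this stratum's, and it only decides whether results are also shown by stratum.

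**The concern.** Effect modification is a statement about the difference between subgroup effects. SAP 6.4 reports each subgroup effect but commits to no estimate of the difference and no measure of its uncertainty. Readers are left to compare the rows of a forest plot, and both common shortcuts mislead. Reading one significant and one non-significant row as a difference finds modification far too often. Requiring the two intervals not to overlap finds it far too rarely.

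At stake is the interpretation of the subgroup results, not the primary result. Subgroup results carry weight in this programme: protocol 2.2 and 4.3 base the choice of population on the no-alteplase stratum of the preceding trial.

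**Working it through.** **Step 1: reproduce the plan's own power.** The documents give no figure for subgroups, so the check starts from the overall design.
- Protocol 9.1: 0.50 vs 0.6114, N = 850, 1:1, one-sided 0.025, O'Brien-Fleming spending with one look at 60%. Recomputed boundaries are Z = 2.669 and 1.981 (stated 2.668 and 1.981). Recomputed power is 90.6% at N = 850, and 91.3% at N = 0.98 × 850 = 833 with 0.614 in place of 0.6114 (stated 91.3%).
- SAP 1.4: N = 680, one look at 75%. Recomputed boundaries are 2.340 and 2.012 (stated 2.34 and 2.012). Power without re-estimation is 82.3% to 83.0% (stated about 82%).

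The design inputs can therefore be carried into the subgroups. Because the SAP (680, up to 1020) and the protocol (850) differ, all three sizes are used.

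**Step 2: within-subgroup significance when the effect is uniform.** Assume 0.50 vs 0.6114 in every subgroup, 1:1 allocation and no covariates.
- log OR = ln[(0.6114 × 0.50)/(0.50 × 0.3886)] = ln(1.573) = 0.453.
- SE in a subgroup of size n = √[1/(n/2 × 0.25) + 1/(n/2 × 0.2376)], where 0.2376 = 0.6114 × 0.3886.
- Power = Φ(0.453/SE − 1.96); the opposite tail is negligible.
- P(exactly one significant) = a(1 − b) + b(1 − a), where a and b are the two subgroup powers.

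At N = 850, 50:50: n = 425, SE = √(0.0188 + 0.0198) = 0.197, power = 0.635. Discordance = 2 × 0.635 × 0.365 = 0.46.

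At N = 850, 20:80: n = 170 gives SE 0.311 and power 0.308; n = 680 gives SE 0.155 and power 0.831. Discordance = 0.308 × 0.169 + 0.831 × 0.692 = 0.63.

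| N | 50:50 | 20:80 | 10:90 |
|---|---|---|---|
| 680 | 50% | 62% | 70% |
| 850 | 46% | 63% | 74% |
| 1020 | 41% | 61% | 75% |

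A direct interaction test has a nominal false-positive rate of 5%. Three listed factors (NIHSS and the two time intervals) are cut at the median and so fall near 50:50 by construction. For the others the documents give no shares, and these splits are assumptions.

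**Step 3: the non-overlap reading.** With equal SEs, two 95% intervals separate only when the difference exceeds 2 × 1.96 SE, while the SE of the difference is √2 SE. The threshold is z = 1.96 × 2/√2 = 2.77, a two-sided test at about 0.006.

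**Step 4: what an interaction test would deliver.** SE of the log ratio of ORs = √(SE₁² + SE₂²).
- N = 850, 50:50: SE = 0.278. The ratio detectable with 80% power is exp[(1.96 + 0.842) × 0.278] = 2.18. Power for a ratio as large as the whole design effect (1.573) is 37%.
- N = 850, 20:80: SE = 0.347, detectable ratio 2.65, power for 1.573 is 26%.
- 50:50 at N = 680 and 1020: detectable ratios 2.39 and 2.04.

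**Step 5: multiplicity.** Across 12 independent tests at 0.05, P(at least one false positive) = 1 − 0.95¹² = 0.46. The listed factors are not independent (age appears twice), so this is a guide only.

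**The case against.** A reader might infer that the plan contains no interaction test. It does contain one, for the 4.5-hour stratum, supported by a Breslow-Day test and reporting by stratum. The gap is confined to the factors in SAP 6.4.

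A reader might also infer that the planned analysis cannot answer its question. That is too strong. For a two-level factor the subgroups are disjoint, so an approximate contrast and its standard error can be worked out from the two reported odds ratios and intervals. The plan simply does not commit to doing so.

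The documents contain no rule that declares modification when one subgroup is significant and the other is not. The discordance figures therefore measure a likely misreading, not the error rate of a planned procedure. They also assume the same 50% placebo response in every subgroup, which is unlikely for age or stroke severity. Both documents label these analyses exploratory, and nothing confirmatory depends on them.

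It is tempting to add that odds ratios from separate logistic models cannot be compared because they are non-collapsible. That argument is weak here: each subgroup model conditions on the same covariate set, apart from a factor such as sex that is constant within its own subgroup.

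The preceding trial is not an example of a subgroup judged without interaction evidence. Protocol 4.3 says that alteplase use was a stratification factor there, and reports evidence of an interaction.

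Finally, the added tests are weak, so a non-significant result could be misread as showing a uniform effect. All of this stands and limits the weight of the point. It does not supply the missing estimate.

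**Conclusion.** The point holds for SAP 6.4: the stated question is effect modification, and no treatment-by-factor estimate or test is specified for any listed factor. If results are read by within-subgroup significance, a uniform effect would appear discordant in about 41% to 50% of 50:50 splits and 61% to 63% of 20:80 splits, against 5% per interaction test. These figures rest on assumed subgroup shares, a common 50% placebo rate, no covariate adjustment, and N from 680 to 1020.

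The documents do not support a claim that interaction is ignored throughout the plan, that the reported figures could never answer the question, or that the trial's main inference is at risk. The primary conclusion and its type I error are unaffected. This is a cheap improvement.

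**What to change.** In SAP 6.4, replace the separate models with one model per factor on the full ITT set: treatment, factor, treatment-by-factor interaction and the primary-analysis covariates. Use a joint test for four-level race. Give the 105-120 kg group the comparator named in the protocol, assigning exactly 105 kg to one side only.

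Show the interaction estimate, its 95% confidence interval and its p-value beside the subgroup effects on the forest plot. Use the scale of the primary analysis and name it, because interaction depends on scale. That scale must first be reconciled: SAP 6.1.3 uses relative risk, protocol Table 9-1 uses a risk difference, and SAP 6.4 uses odds ratios.

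State that the tests are exploratory, unadjusted for multiplicity (about a 46% chance of at least one false positive across 12 independent tests) and low-powered (at N = 850 with a 50:50 split, a ratio of odds ratios of about 2.2 is needed for 80% power), so that a non-significant result is not evidence of a uniform effect.

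The cost is a change of SAP wording and the matching table and figure shells. No new data are needed, and fewer models are fitted.

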6.5 Pharmacokinetic Analyses

PK samples will be collected at baseline and at multiple time points after the complete dose was administered from up to 100 subjects enrolled at a subset of sites in Canada and the US.

Actual sampling time-points will be recorded and used for PK calculations. If data permit, the following PK parameters for nerinetide will be calculated at the end of the study by standard noncompartmental methods for all subjects with PK samples:

- AUC0-t: Area under the concentration-time curve from time zero to time of last measurable concentration
- AUC0–inf: Area under the concentration-time curve from time zero to infinity
- Cmax: Maximum plasma concentration observed after dosing
- Tmax: Time to occurrence of Cmax
- t¹/₂: Terminal elimination half-life

Samples with no detectable nerinetide will be excluded from analysis (placebo).

Descriptive statistics will be calculated for nerinetide plasma concentrations and for all PK

parameters (AUC_{0-t}, AUC_{0- ∞}, C_{max}, T_{max}, t_{1/2}).

PK results at all timepoints will be listed for the Nerinetide arm by subject.

6.6 Outcome Analysis for 1-Year Sub-Study

The outcomes of the 1-Year Sub-Study are intended to be supportive of the 90-day outcomes of the main study. The analysis population will be comprised of participants with a valid consent for the 1-year sub-study in the relevant jurisdiction. Missing data will be imputed as per Section 4.3 except that for subjects who are successfully contacted (i.e., not deceased) but who cannot complete the telephone interview (e.g., due to dysphasia, a language barrier, or incapacity) will have their outcomes estimated by the interviewer. A summary table will specify the differences between the population analyzed in the main study and the 1-year sub-study, including deaths, losses to follow-up and withdrawal of consent.

The primary outcome is the proportion of subjects with independent functioning on the modified Rankin Scale (mRS), as defined by a score of 0-2) at 1 year.

The secondary outcomes include:

- A reduction in mortality rate, as defined by event rate (%) for mortality over the 1-year study period.
- The proportion of subjects with independent function on activities of daily living defined on the modified Barthel Index (BI) with a score of \geq 95 at 1 year.
- Health-related quality of life, as measured by the EQ-5D-5L at 1 year.

6.6.1 mRS at 1 Year

The mRS will be assessed as per the protocol. It will be dichotomized, analyzed and reported as in the primary efficacy analysis.

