2 ANALYSIS POPULATIONS

This study is designed to address a population of adults 18 years and older harboring an acute ischemic stroke who are selected for endovascular revascularization without intravenous or intraarterial thrombolytic therapy who will receive a single, 2.6 mg/kg (up to a maximum dose of 270 mg) intravenous dose of nerinetide or placebo.

2.1 This is a global trial being conducted under the same protocol at clinical sites in different countries in accordance with the national legislation of the country in which the trial is carried out. Following the completion of the study and provided that the requirements of 21CFR 312.120 are met, data from all study sites will be pooled for the purpose of analyses in this statistical analysis plan.Intent-to-Treat (ITT) Population

The primary efficacy analysis will be conducted on the ITT population, defined as all subjects randomized into the trial with grouping by randomized treatment, regardless of treatment actually received. Deceased subjects will be included in the ITT population with a mRS score of 6, NIHSS of 42 and Barthel Index of 0. An ITT analysis will also be conducted for the secondary endpoints, with subjects grouped according to the randomized (intended) treatment.

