4.3.1 Imputation of Mortality and Worsening of Stroke

For the analysis of rate of mortality, for participants for whom the mortality status is not known at Day 90:

- if they were alive at Day 30, then the subject will be imputed as alive at Day 90
- if both the Day 30 and Day 90 mortality is status is missing, the participant will be imputed as Dead at Day 90.

Worsening of stroke data will be imputed similarly:

- if it's unknown whether the subject experienced worsening of stroke by Day 90 while they did not report any worsening of stroke by Day 30, then the subject will be imputed as not experiencing worsening of stroke at Day 90.
- if both worsening of stroke status is unknown at both Day 30 and 90, then the subject will be imputed as experiencing worsening of stroke at Day 90.

No imputation will be done on the missing one-year follow-up mortality data.

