The shift parameters that result in a reversed study conclusion (i.e. from statistically significant to non-significant) will be flagged. Alternate series of shift parameters may be applied based on the actual data.

The missing mRS data at one-year follow-up will be handled according to below:

- If subjects are known to be dead before or at one-year follow-up visit, mRS will be assigned a score of 6 and counted as non-responders.
- Other missing data not due to death will be imputed by the multiple imputation method as described above.

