4.3.3 Imputation of NIHSS and BI data

No missing NIHSS or BI data due to death. Deceased participants will be assigned scores 42 on the NIHSS and 0 on the Barthel Index (BI) and be counted as non-responders.

Missing NIHSS or BI data at Day 90 will be imputed using the last observation carried forward (LOCF) imputation as follows:

LOCF: Participants who are missing NIHSS or BI endpoint data at Day 90 will have the last

recorded score carried forward, provided that this score was obtained at the Day 30 visit or later. Otherwise, the missing NIHSS or BI will be imputed to the median score obtained at Day 90 in the trial.

For missing BI data at one-year follow-up visit:

- If the subjects are known to be dead before or at one-year follow-up visit, BI will be assigned a score of 0.
- Other missing BI data not due to death will be imputed to the median score obtained at oneyear follow-up in the trial.

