	Day 90 EQ-VAS	ANCOVA, ITT, OC	N/A	N/A
1 Year	mRS Responder (≤2 vs. >2)	Adjusted log-binomial regression model, ITT, MI	N/A	N/A
	Day-90 Mortality	Adjusted log-binomial regression model, ITT, OC	N/A	N/A
	Barthel Index	Adjusted log-binomial regression model, ITT	N/A	N/A
	EQ-VAS	ANCOVA, ITT, OC	N/A	N/A

*For analyses using the adjusted log-binomial regression model, a Poisson model with robust variance will be used if the log-binomial model fails to converge

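### The 1-year analyses are restricted to participants with sub-study consent yet labelled ITT; the population, and the handling of deaths and non-consent within it, need to be settled

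*Combined protocol and SAP*

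**What the plan says.** **Population.** SAP 6.6 limits the 1-year analysis population to "participants with a valid consent for the 1-year sub-study in the relevant jurisdiction". Protocol 9.3.2.2 carries the same restriction. In SAP Table 4, however, all four rows of the 1-year block are labelled ITT. The mRS responder row reads "Adjusted log-binomial regression model, ITT, MI". The mortality row, printed there under a Day-90 label, reads "Adjusted log-binomial regression model, ITT, OC". The ITT population in SAP 2.1 is "defined as all subjects randomized into the trial with grouping by randomized treatment, regardless of treatment actually received", with no consent condition.

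**Deaths and missing data at 1 year.**
- mRS (SAP 4.3.2): "If subjects are known to be dead before or at one-year follow-up visit, mRS will be assigned a score of 6". Other missing values go to multiple imputation (MI).
- Barthel Index, BI (SAP 4.3.3): "If the subjects are known to be dead before or at one-year follow-up visit, BI will be assigned a score of 0". Other missing values take the trial median at 1 year.
- Mortality (SAP 4.3.1): "No imputation will be done on the missing one-year follow-up mortality data".

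Table 4 shows N/A for sensitivity and supportive analyses in every 1-year row. SAP 6.6 plans a descriptive table of how the main-study and 1-year populations differ, and names deaths, losses to follow-up and consent withdrawal.

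**Consent.** The protocol's Schedule of Activities (Table 1-1) lists initial and regained-capacity consent and no separate sub-study item. Protocol 10.6.1 allows enrolment on the investigator's decision where consent is not feasible and the law permits. Protocol 5.5.2 foresees death before regained-capacity consent.

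**The concern.** The two definitions give different denominators for every 1-year result, and a programmer has to choose between them. The rule that the SAP prevails over the protocol (protocol 9.3) does not help, because the conflict lies inside the SAP.

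The choice matters because consent status may be settled after randomization and may depend on how the participant fares. Someone who declines, or who never becomes able to consent, is likely to differ in outcome from someone who agrees. A consent-based set therefore gives up the protection of randomization, and the planned summary table describes that loss without correcting it. If early deaths also fall outside the set, the mRS 6 and BI 0 rules never reach them: nothing in SAP 4.3 extends those rules to people outside the population defined in 6.6.

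**Working it through.** **Step 1. The plan's own figures.** The documents give no sample size, power or expected rate for the 1-year analysis, so there is no 1-year figure to reproduce. The stated Day 90 power of 91.3% is not in dispute: 850 less 2% is 833, and a two-proportion calculation with 50% vs 61.4% returns 91.3%.

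**Step 2. Who leaves under 6.6.**
- *Living non-consenters.* Excluded by the text of 6.6. Under Table 4's ITT and MI label, their 1-year mRS would instead be imputed.
- *Deaths before sub-study consent.* Excluded only if that consent is taken after enrolment. If initial consent covers the 1-year contact, they stay in and score mRS 6 and BI 0.

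**Step 3. Illustration for early deaths.** Inputs are from protocol 2.1.5 (ESCAPE-NA1, no-alteplase stratum, Day 90): responders 59.4% vs 49.8%; mortality reduction 7.5 points absolute, 39.7% relative.
- Implied placebo mortality: 0.075 / 0.397 = 18.9%.
- Implied nerinetide mortality: 18.9% − 7.5% = 11.4%.

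Two assumptions are added: these Day 90 rates stand in for 1-year rates, and a fraction f of early deaths is lost in both arms. With responder rate r and mortality m, the retained set has responders r / (1 − f·m) and deaths (1 − f)·m / (1 − f·m).

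| f | Responders, nerinetide vs placebo | Difference (points) | Relative risk | Mortality difference to Day 90 (points) |
|---|---|---|---|---|
| 0 | 59.4% vs 49.8% | 9.6 | 1.19 | −7.5 |
| 0.5 | 63.0% vs 55.0% | 8.0 | 1.15 | −4.4 |
| 1 | 67.0% vs 61.4% | 5.6 | 1.09 | 0 |

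For example, at f = 1: 0.594 / 0.886 = 67.0% and 0.498 / 0.811 = 61.4%.

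If mortality were equal in the arms (15% assumed), the relative risk would stay at 1.19 at any f, and the risk difference would rise to 0.096 / 0.85 = 11.3 points at f = 1. Bias in the relative risk, the SAP's effect measure, therefore needs the loss to differ by arm. If nerinetide lowers mortality, the bias runs against it.

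**Step 4. Illustration for living non-consenters.** Assume no true effect and 50% responders overall, a share q not consenting, and a responder rate s among them. The consented set then shows (0.5 − q·s) / (1 − q).
- q = 20% vs 10%, s = 20%: 0.46 / 0.80 = 57.5% against 0.48 / 0.90 = 53.3%, a false difference of 4.2 points.
- q = 10% vs 5%, s = 30%: 0.47 / 0.90 = 52.2% against 0.485 / 0.95 = 51.1%, a false difference of 1.2 points.
- Equal q and s in both arms: 0.

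The sign follows the arm with more non-consent. In a blinded trial with no true effect, unequal non-consent would arise mainly by chance, so these figures show sensitivity rather than an expected bias.

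**The case against.** The strongest objection is that the loss of early deaths is inferred. No text says that sub-study consent is separate from, or later than, initial consent. The 1-year contact belongs to the same protocol and closes the study (protocol 4.5), and initial consent may come from the participant or a legal representative. Nothing says that death before regained-capacity consent voids the initial consent, and protocol 7.2 retains data already collected. The mRS 6 and BI 0 rules, and a mortality endpoint spanning the whole year, suggest that deaths were meant to count. The consent forms are not among the documents reviewed, so silence on timing cannot be held against the plan. All of this stands, and it makes the early-death part conditional.

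It is also true that the 1-year outcomes are described as supportive and lie outside the fixed testing sequence, that the consent limit may reflect legal constraints by jurisdiction, and that exclusion of whole jurisdictions need not bias the comparison.

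A reader might go further and infer that early deaths will be dropped and the effect cut from 11.4 to 7.6 points (0.614 / 0.886 − 0.50 / 0.811 = 69.3% − 61.7%). The documents do not support this. It joins the earlier trial's mortality to this trial's design response rates, and it assumes that no one who died by Day 90 had valid consent.

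None of these points removes the conflict between 6.6 and Table 4, or the exclusion of living non-consenters.

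**Conclusion.** The inconsistency is established: one set of analyses has two incompatible populations. Exclusion of living non-consenters follows from 6.6 as written, with no planned analysis to show its effect. Exclusion of early deaths is possible but not shown.

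If it occurs, the responder difference in the illustration falls from 9.6 points to 8.0 with half of the early deaths lost and to 5.6 with all lost. This rests on the earlier trial's Day 90 rates holding at 1 year and on an unknown fraction lost. If initial consent covers the 1-year contact, the loss is near zero.

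The Day 90 conclusion and the type I error rate are untouched. What is at risk is the credibility of the long-term supportive evidence, so the point should be fixed but does not threaten the trial.

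**What to change.** Reconcile SAP 6.6 and protocol 9.3.2.2 with SAP Table 4:

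- **Population.** Make the main 1-year analysis all randomized participants. If law requires a limit, use all randomized in jurisdictions where the sub-study is approved, and do not label that set plain ITT.
- **Known deaths.** Carry deaths already recorded in the main trial into the 1-year analysis as deaths, mRS 6 and BI 0, whatever the sub-study consent status.
- **mRS in living non-consenters.** Treat as missing and use the SAP's MI. The example code in SAP 4.3.2 stops at Day 90, so write out a 1-year step with Day 90 status as a predictor.
- **Mortality.** Keep the no-imputation rule, but in the time-to-death analysis censor non-consenters when last known alive. Read the observed-case proportion beside it, since that proportion keeps known deaths but drops living non-consenters.
- **BI.** Replace the median rule with the same MI approach, or report observed cases.
- **Consented-only set.** Keep it as a supportive analysis.
- **Consent timing.** State when and how sub-study consent is taken.

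The cost is revised wording in both documents and modest extra programming. The main-trial deaths are already in the database, though the sponsor should confirm against the consent forms that this use is covered. The downside is reliance on missing at random for non-consenters' mRS, and on non-informative censoring for their survival.
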